The sample size calculations are based on estimates of 10-year IDFS with an annual hazard rate of 0.0223. A sufficient number of patients is sought to provide 80% power using a two-sided 0.05-level test to detect a 25% reduction in the risk of an IDFS event (hazard ratio=0.75). A total of 379 events are required. With an estimated 5% drop-out at 5 years (annual rate 0.0103), this is estimated to be achieved by a total recruitment of 3,360 participants and a $6\frac{1}{2}$ years follow-up. The sample size estimate is

based on inclusion for 3 years, a median follow-up of 6½ year, that is 5 years of additional follow-up after the 3 years of inclusion.

TRANSLATIONAL STUDIES

BLOOD SAMPLES

Trial participants are asked for blood samples collected at baseline, after one and two years of study treatment, respectively, and in case of early withdrawal or recurrence while on study treatment. Particularly for neoadjuvant patients, an additional blood sample will be drawn at the time of stopping chemotherapy/prior to surgery. Samples are stored in a research biobank established for this study. Circulating biomarkers will be analyzed for their predictive and prognostic value. Samples are stored as plasma, serum, buffy coat, and whole blood at minus 80-degree Celsius at the Departments of Biochemistry of participating hospitals and final storage at the Danish Cancer Biobank.

TUMOR TISSUE SAMPLES

Archived tumor tissue from the primary breast tumor will be sampled in tissue micro arrays, which are then stores in a research biobank. Triplicate cores of 1 mm in diameter will be sampled from the donating tumor block and mounted in a recipient paraffin block, which will be able to host tumor cores from 50-60 tumors per paraffin block. Primary tumor tissue will be analyzed for the expression of cholesterol associated biomarkers, including i.e. HMGCR, LDL-receptor, and CYP27A1. One of the tumor tissue cores will be sampled for RNA-extraction and further gene expression analyses using the Illumina Platform. Tumor tissue analyses will allow for identification of prognostic and treatment predictive factors and pave the way for more personalized (neo)adjuvant treatment.

TABLE OF CONTENTS

1		BAC	CKGR	OUND AND INTRODUCTION	11
	1.1	1	Вас	kground disease information	11
	1.2	2	Bac	kground therapeutic information	14
2		OBJ	ECT1	IVES OF THE TRIAL	15
	2.1	1	Prin	nary objective	15
	2.2	2	Sec	ondary objectives	15
	2.3	3	End	points	15
3		PAT	IENT	SELECTION CRITERIA	16

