6.4 After the end of treatment (follow-up)

The follow-up includes assessment of clinical events (recurrences) and overall survival at a yearly basis up to 10 years after inclusion in the study. Patients are followed in the clinic according to the time points for clinical routine visits (up to 10 years depending on menopausal status). Clinical events are recorded at a yearly basis into the DBCG CRF database.

To ensure detection of potential long-term effects and side effects of STUDY TREATMENT, linkage to medical records and the national cancer - and death registries up to 20 years after diagnosis will facilitate long-term follow-up and detection of late recurrences and other secondary cancers. Other possible late side effects will be identified through linkage to the Hospitalization Registry.

Importantly, patient reported outcomes are to be reported yearly through a RedCap-based model up to 10 years after study inclusion.

6.5 Summary table 1

Study procedures for the randomized cohort described in the following table:

Required Investigations	Baseline (T1)	3 months (+/- 14 days) (T2)	6 months (+/- 14 days) (T3)	1 year (+/- 14 days) (T4)	2 years (+/- 14 days) (T5)	Yearly, (+/- 28 days) 3-10 years (T6)
Inclusion - exclusion criteria (DBCG)	X					
Informed consent	X					
Randomization (DBCG)	X					
CRF Master flow (DBCG)	X	X ³	x ³⁴	X ³⁴	X ³⁴	X ⁴
CRF Master AE (DBCG)	X	X ³⁴	X ³	X ³⁴	X ³	
STUDY MEDICATION START/ADHERENCE (DBCG)	X	Х	Х	Х	Х	
Patient Reported Outcome (RedCap)	X	X	X	X	X	X
Pathological response (Only patients in neo- adjuvant cohort)			Х			
HCG⁵(serum or urine)	X					
Hepatic (ALT) function	X ²	Х		Х	Х	
Renal (creatinine) function	X ²					
Creatine kinase ¹	(X)					
Translational blood samples	X		(X neoadjuvant cohort patients)	X	X	
Translational tumor tissue samples from existing tissue	X		(X neoadjuvant cohort patients)			

^{1.} Predisposing factors for rhabdomyolysis, including hypothyroidism, reduced renal function, any muscle – or liver disease, or excessive alcohol consumption above 14 drinks/week AND creatine kinase (CK) measured to more than five times the upper limit (CK only measured in case of predisposing factors).

- 2. Blood samples are allowed to be taken up to 28 days before T1
- 3. Either done by phone interview or attendance at the clinic
- 4. Data collected from the patient file
- 5. Only fertile women

6.6 Summary table 2

Study procedures for the observational cohort are described in the following table:

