10 TRANSLATIONAL RESEARCH

Translational research will be performed in co-operation with the laboratory units at the trial sites participating in this protocol.

Tumor samples will be treated and stored according to current research ethical practice in Denmark in a research biobank assigned for this trial. Blood samples of a total of 30 ml/time are drawn at three time points: at baseline and at 1 and 2 years after inclusion. And for patients in neo-adjuvant cohort also a

blood sample at 6 months. Frozen blood samples will be stored in a research biobank at the Danish Cancer Biobank. Potential left-over blood after the analyses for this study, are stored in the research biobank in the Danish Cancer Biobank for future, not yet specified, research.

Pathological samples are stored according to clinical routines at the Departments of Pathology affiliated with the trial sites although one tissue block is set aside for the MASTER study, and upon completion of trial enrollment, triplet sample cores of 1 mm in diameter are arranged in a tissue microarray (TMA) and stored in a research biobank at the DBCG biobank for future research (RH-2015-122, I-Suite nr: 03903). The biological samples will be used for analyses in relation to the following translational endpoints:

Tumor tissue sampled at baseline (for neoadjuvant patients both at diagnosis and at surgery)
will be analysed for biomarkers of prognosis and treatment prediction; i.e. HMGCR, LDL-R
expression along with HMGCR down-stream products in the mevalonate pathway (e.g.
farnesyl-pyrophosphatase, geranylgeranyl-pyrophosphatase and phosphorylated-ERK, the
latter indicating an activated Ras pathway).

Serum, plasma and whole-blood collected at baseline and during follow-up will be analyzed for prognostic and predictive markers, i.e. LDL, HDL, cholesterol, triglycerides, Apo-A, and Apo-B, HMGCR SNP's, circulating antibodies and circulating tumor-DNA (ctDNA), the latter to monitor the burden of circulating ctDNA according to treatment response as well as to investigate specific mutations for their potential treatment predictive value, i.e. TP53 mutations.

The data center for the translational parts of this trial is housed at the Department of Oncology, Aarhus University.

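### The extra neoadjuvant research blood sample is timed by surgery in the synopsis but by the calendar (6 months) in section 10 and Table 1, so it can be drawn after the tumour has been removed

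*Protocol*

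**What the plan says.** The synopsis (Translational studies, Blood samples) plans research blood at baseline and after one and two years of study treatment, and in case of early withdrawal or recurrence on treatment. For neoadjuvant patients it adds that "an additional blood sample will be drawn at the time of stopping chemotherapy/prior to surgery".

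Section 10 counts its blood samples from inclusion: "at baseline and at 1 and 2 years after inclusion". For the neoadjuvant cohort it adds a "blood sample at 6 months", without mention of chemotherapy or surgery.

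Table 1 (section 6.5) enters the same draw as "X neoadjuvant cohort patients" in the column headed "6 months (+/- 14 days) (T3". No footnote links it to the end of chemotherapy or to surgery.

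Two neighbouring entries matter less. Table 1 has a neoadjuvant entry at T3 in the row "Translational tumor tissue samples from existing tissue", whereas section 10 says that tissue is taken "for neoadjuvant patients both at diagnosis and at surgery". Table 1 also marks the row "Pathological response (Only patients in neo- adjuvant cohort" at T3, as far as the extracted table can be read.

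**The concern.** One draw has two definitions: one names an event, the other a date. They agree only if surgery happens to follow the T3 visit. Sites work from the visit schedule, so the calendar definition is the one likely to be applied.

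The difference matters for tumour-derived markers. Section 10 plans to follow ctDNA according to treatment response. Before surgery, ctDNA reflects a tumour still in place under treatment. After surgery, it reflects whatever remains once the tumour is out. If both kinds of draw are stored as one T3 value, the relation to response is blurred, and the blurring depends on regimen and entry time. The other scheduled draws are at baseline, one year and two years, so this is the only scheduled on-treatment draw likely to precede surgery. Once missed, it cannot be recovered.

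**Working it through.** **Step 1: compare the texts.** For blood, the synopsis stands against section 10 and Table 1. The first two are plain prose, so a broken table cannot explain the difference. For tissue, the mismatch lies between Table 1 (T3) and section 10 (at surgery); the synopsis gives no time beyond archived tissue. For pathological response, only Table 1 gives a time; the synopsis lists the endpoint without one, and section 10 does not mention it.

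**Step 2: the T3 window.** Six months = 365.25 / 2 = 182.6 days. With +/- 14 days this is 168.6 to 196.6 days, that is 24.1 to 28.1 weeks after inclusion.

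**Step 3: the date of surgery.** The protocol states neither the chemotherapy length (L) nor the gap to surgery (g), so both are assumptions: L = 18 or 24 weeks, g = 3 or 5 weeks. With entry at the start of chemotherapy, surgery falls at week L + g.

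| L (weeks) | g (weeks) | Surgery (week) | T3 window relative to surgery |
|---|---|---|---|
| 18 | 3 | 21 | 3.1 to 7.1 weeks after |
| 18 | 5 | 23 | 1.1 to 5.1 weeks after |
| 24 | 3 | 27 | 2.9 weeks before to 1.1 weeks after |
| 24 | 5 | 29 | 4.9 to 0.9 weeks before |

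Overall the window runs from about 5 weeks before to about 7 weeks after surgery. With an 18-week course every T3 draw is post-surgical. With a 24-week course the window lies mostly or wholly before surgery.

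**Step 4: wider assumptions.** With g from 2 to 6 weeks, a course of 12 or 18 weeks puts surgery at weeks 14 to 24, before the window opens. A 24-week course puts it at weeks 26 to 30, inside the window or after it.

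**Step 5: entry time.** Each week between randomization and the start of chemotherapy moves surgery one week later on the T3 clock. In the 18-week rows, surgery would fall after the window opens only if that delay exceeded 24.1 - 23 = 1.1 weeks (g = 5) or 24.1 - 21 = 3.1 weeks (g = 3). Conversely, each week of chemotherapy given before inclusion moves surgery one week earlier.

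**The case against.** The strongest reply is that 6 months is shorthand for the end of a neoadjuvant course. With 24 weeks of chemotherapy and a 5-week gap the two definitions do coincide. That stands for this case. It does not make the texts equivalent, and nothing in section 10 or Table 1 tells a site to bring the draw forward when surgery comes earlier.

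A second reply is that the analysis could separate draws before and after surgery. Section 13.1 says that the CRF system already collects surgery and oncological treatment data, and Table 1 records the start of study medication. This largely stands: misclassification can be repaired if the draw date is known. A pre-surgical sample that was never drawn cannot be.

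Third, lipid levels are systemic, so a lipid value does not lose its meaning once the tumour is out. This stands, and the point is confined to tumour-derived markers such as ctDNA.

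A reader might also infer that blood, tissue and pathological response are all placed at 6 months in the body and at surgery in the synopsis. The protocol does not support that. Section 10 puts tissue at surgery, and the synopsis gives no time for surgical tissue or pathological response. The tissue comes from existing material, so those T3 entries may only be nominal recording points.

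**Conclusion.** The contradiction is established for one item, the extra neoadjuvant blood draw, and must be reconciled. Under the stated assumptions the T3 draw ranges from about 5 weeks before to about 7 weeks after surgery, so for a given regimen and entry time some or all draws can be post-surgical. This already holds when entry is at the start of chemotherapy.

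It is tempting to say that many samples will be too late. The share cannot be derived: the protocol gives no chemotherapy length, interval to surgery, distribution of entry times or number of neoadjuvant patients.

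It is also tempting to assume entry halfway through chemotherapy. Surgery would then be at weeks 12 to 17 (9 + 3 to 12 + 5), and the whole window 7 to 16 weeks after it. But the synopsis defines the early cohort as randomized before therapy starts, and the section 12 schedule, which might suggest otherwise, cannot be read reliably as extracted. The conclusion does not rest on it.

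The tissue mismatch between Table 1 and section 10 is a matter of clarity, and no effect on the pathological response endpoint is shown. The primary endpoint, IDFS, and its 379-event calculation are untouched.

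**What to change.** - In Table 1 and section 10, move the extra neoadjuvant blood draw from 6 months to the end of neoadjuvant chemotherapy, before surgery, in line with the synopsis.
- Add a footnote to Table 1 that the neoadjuvant tissue and pathological response entries refer to the surgical specimen and that T3 is only where they are recorded, if that is what is meant.
- Record the date of the draw, so that it can be related to the surgery and study-medication start data already collected. Draws already taken at 6 months can then be classified as before or after surgery.

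The cost is an amendment to one table and one paragraph, with the same number of samples. The draw may no longer coincide with the T3 contact. Little is lost by that: T3 has no hepatic blood test (section 5.1.3 sets these at baseline and 3, 12 and 24 months), and Table 1 allows its CRF contact by phone.

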1 BACKGROUND AND INTRODUCTION

1.1 Background disease information

Breast cancer is the most common malignancy among women worldwide and accounts for more than one million incident cases each year (1, 2). In Danish terms, that is a yearly incidence of around 4,600 women diagnosed with breast cancer and a lifetime risk of 10-15% (Nordcan, 2019). Over the past 20 years the breast cancer incidence has increased globally (3) which corresponds to an increase of 1.4% per year in Denmark (Nordcan, 2018). Breast cancer treatment includes a wide range of both local and systemic approaches applied in different phases of the disease—surgery, radiotherapy, chemotherapy, endocrine therapy, and anti-HER2 therapy. Neo-adjuvant systemic therapy (NACT) is recommended to patients with large tumors (2-5 cm) and to patients who are technically inoperable (locally advanced breast cancer, LABC). Adjuvant therapy is provided patients with radically operated non-metastatic disease and comprises chemotherapy, radiation therapy, and in the case of estrogen receptor (ER) positive breast cancer, endocrine therapy is prescribed for 5-10 years, tamoxifen to pre-menopausal women, and aromatase inhibitors to postmenopausal patients. Anti-HER2 therapy with trastuzumab/pertuzumab is approved in the (neo)adjuvant setting for patients with HER2 amplified breast cancer.

Breast cancer mortality has improved in developed countries with a decrease of 14% from the 1970s to the 1990s (3). However, breast cancer still remains the leading causes of cancer death among women (2). The prognosis for Danish breast cancer patients corresponds with a relative 1-year survival of 97% and a 5-year survival of 87% (Nordcan, 2015). The risk of breast cancer is indeed age-related and less than 1% of breast cancer patients are younger than 30 years at diagnosis (4). The incidence increases along with age and peaks at the age of 65 years (Nordcan, 2015).

Clinical evidence of statins beneficial effects in breast cancer

Cholesterol-lowering statins (HMG-CoA reductase inhibitors) have received substantial scientific attention as cancer-inhibiting drugs. One of the first epidemiologic studies on this topic reported an imprecisely-measured protective association between statin use and breast cancer recurrence in a cohort of almost 2,000 women (hazard ratio [HR]=0.67, 95% CI: 0.39, 1.13). In an additional Danish study, [name], [name] $et\ al$ measured this association with much higher precision in a cohort of over 18,000 Danish breast cancer patients, finding nearly identical reduction in recurrence rate among women who took statins (HR_{adj}=0.73, 95% CI: 0.60, 0.89). Since publication of these initial studies, several other groups have replicated the protective association in a variety of source populations and with a variety of study conditions (7-9). A recent systematic review and meta-analysis of the evidence base reported a summary relative risk of 0.64 (95% CI: 0.53 to 0.79) (10).

Most recently, Drs. [name], [name] and colleagues published a study nested in the Breast International Group 1-98 trial (BIG 1-98), in which DBCG was a key partner and important trial contributor. The aims of the study were to (1) characterize patterns of cholesterol-lowering medication (CLM) initiation according to adjuvant endocrine therapy received (tamoxifen or letrozole), and (2) evaluate whether initiation of CLM (predominantly statins) during endocrine therapy was associated with clinical outcome. The incidence of CLM was higher among women taking letrozole, whereas cholesterol levels decreased over time among women taking tamoxifen, irrespective of CLM use. Initiation of CLM during endocrine therapy was associated with improved breast-cancer-free interval (HR=0.76, 95% CI: 0.60 to 0.97) and distant-recurrence free interval (HR=0.74, 95% CI: 0.56 to 0.97) (11). This study was the first to support the beneficial effect of statins on breast cancer outcome that is nested within a large, international, randomized clinical trial of modern adjuvant endocrine therapy.

Calls for clinical trials of statins in the breast cancer adjuvant setting

Given the compelling evidence supporting a protective effect of statins on breast cancer recurrence, calls for clinical trials have appeared in several prominent journals. One of these calls came from a paper authored by Drs. [name], [name], and colleagues, which summarized the preclinical and epidemiologic evidence for a beneficial effect of statins in breast cancer survivors, and recommended design features for a future adjuvant clinical trial (12).

Molecular basis for statin use as breast cancer therapeutic agents

Statins are routinely used to treat hyperlipidemia but may also have antineoplastic effects. The target for

statins, HMGCR, is a transmembrane glycoprotein found in the endoplasmic reticulum in all cells. HMGCR activity controls the mevalonate pathway which, in addition to cholesterol, produces steroid-based hormones and non-sterol isoprenoids (Figure 1) (12, 13). Inhibition of hepatic HMGCR causes reduced intracellular cholesterol levels in hepatocytes. This in turn triggers up-regulation of low-density lipoprotein cholesterol (LDL-C) receptors to scavenge cholesterol from the serum to support cell growth and division. Serum levels of LDL-C consequently plummet, reducing the rate of adverse cardiovascular events in statintreated individuals (14). Cellular cholesterol levels and HMGCR activity are maintained via tightly regulated feedback mechanisms, whereas extracellular serum cholesterol concentrations vary (15). In addition to reducing LDL-C production, blocking the mevalonate pathway interrupts synthesis of the isoprenoids geranylgeranyl pyrophosphate (GGPP) and farnesyl pyrophosphate (FPP) (12, 13). Isoprenylation of proteins by GGPP and FPP enables subcellular localization and intracellular trafficking of membraneassociated proteins that are essential for the cell (16). GGPP and FPP post-translationally prenylate a host of proteins—including the oncogene products Ras, Rac, and Rho—to enable their full function.(16-18) The isoprenoids demonstrate tumor-suppressive properties as regulators of important processes in cancer such as proliferation, migration, and angiogenesis (13, 19). Comprehensive analysis of statin-induced changes in tumor cell lipid profiles may reveal the dominant pathways through which statins attenuate tumor promotion (20).

Highly proliferative cells (such as cancer cells) must rapidly produce lipid bilayer membranes, requiring increased cholesterol biosynthesis (21). While the cholesterol biosynthesis pathway is tightly regulated in normal cells, it may be dysregulated in cancer cells (22). It has been implied that HMGCR is a metabolic oncogene, and that dysregulation of the mevalonate pathway promotes transformation (23). In addition, high mRNA levels of HMGCR and other mevalonate pathway genes were associated with impaired prognosis for breast cancer patients (23). This finding was recently validated in two large breast cancer datasets (24).

The mevalonate pathway is a possible therapeutic target for tumors with mutations of the tumor suppressor p53 (25, 26). The p53 protein, encoded by the TP53 gene, is dubbed "the guardian of the genome" due its tumor-suppressing activities. These activities, triggered by DNA damage, include activation of DNA repair mechanisms, initiation of growth arrest at the G1/S boundary, and induction of apoptosis if repair fails. The mevalonate pathway is both necessary and sufficient for the phenotypic effects of mutant p53 on breast tissue architecture, and mutant p53 associates with sterol gene promoters (25). In a 3-dimensional culture model, mutant p53 up-regulated mevalonate pathway genes in breast cancer cells, leading to disordered, invasive morphology (25). In the same model, depletion of mutant p53 by RNA interference caused reversion to normal morphology. Remarkably, the addition of clinically achievable concentrations of statin to the culture system resulted in marked reductions in tumor cell growth, induction of apoptosis, and reversion to normal morphology in the various breast cancer cell lines tested. (25) The beneficial effects of statin were negated when the mevalonate pathway products GGPP and FPP were simultaneously added to the culture medium. The p53 effect is likely modulated by sterol regulatory element-binding proteins (SREBPs) and tied to the YAP/TAZ effectors of the Hippo signaling pathway (27). YAP/TAZ activity is also controlled by Rho GTPases, which are dependent on prenylation for activation (28). Therefore, overexpression of genes encoding p53, SREBPs, mevalonate pathway genes, and the YAP/TAZ transcriptional regulators may identify breast tumors that will be sensitive to statin treatment.

A large number of *in vitro* and *in vivo* cancer studies with statins have been performed, with many more underway. So far, these models have shown that statins decrease proliferation and increase apoptosis of breast cancer cells (29, 30). The biological mechanisms for these actions are not yet fully elucidated. Our previous work demonstrated that HMGCR is differentially expressed in human breast cancer samples and holds prognostic value (31, 32). HMGCR may also predict tumor response to endocrine treatment (33), as well as to statin treatment, the latter demonstrated in a recent phase II clinical trial (ClinicalTrials.gov Identifier: NCT00816244) (34). Other *in vitro* studies demonstrated substantial statin-induced increases in HMGCR expression (35), and atorvastatin induced HMGCR up-regulation when assessed with a novel, well-validated monoclonal HMGCR antibody (24). Additionally, *in vivo* studies suggest that HMGCR activity is higher in mammary tumors compared with normal mammary glands, and that tumors are resistant to feedback regulation by sterols (36).

If statins do target the mevalonate pathway in cancer cells within a tumor, the lowering of intracellular cholesterol may lead to lowered intra-tumoral autocrine hormone production, as cholesterol is fundamental for all steroid hormone synthesis. Interestingly, one study has reported that atorvastatin and its metabolites

are detectable in human breast samples following oral administration (37), indicating that direct inhibition of HMGCR may occur in breast tumors. Most relevant for an endocrine responsive disease such as estrogen receptor (ER)-positive breast cancer, statin treatment reduces levels of the cholesterol metabolite 27-hydroxy cholesterol (27HC) (38). 27HC acts as an ER ligand, potentiating ER-dependent tumor growth (39-42). Interestingly, 27HC can agonize both the ER and the liver X receptor (LXR) to drive breast tumor proliferation (39, 40), and it promotes metastasis through interactions with myeloid immune cells.(43) The cholesterol biosynthesis pathway was recently shown to be up-regulated in ER-positive breast cancer cell lines that are resistant to estrogen deprivation (44, 45), suggesting that dysregulation of cholesterol biosynthesis may be a mechanism of endocrine resistance in hormone receptor-positive breast cancer (44, 45). Chronic estrogen deprivation in ER-positive breast cancer cells seems to stabilize the epigenetic activation of the mevalonate pathway and cholesterol biosynthesis, (45) and this leads to the accumulation of other ligands (such as 27HC), which potentiate ER signaling in the absence of estrogen, consequently driving the activation of genes that promote a proliferative and invasive cell phenotype (45).

To summarize, cancer cells depend on cholesterol for continued growth and survival. Therefore, attenuating cholesterol biosynthesis seems to be a promising anti-cancer strategy. Of note, rapidly proliferating cancer cells have an increased cholesterol demand to enable cell membrane synthesis (21, 46). By lowering plasma levels of cholesterol and 27HC, their availability for use by cancer cells is consequently lowered. Additionally, direct inhibition of HMGCR by statins depletes intratumoral reserves of isoprenoids, which are key regulators of cancer cell proliferation and metastasis. Ongoing studies are exploring additional roles that cholesterol, cholesterol metabolites, and statins play in breast tumor promotion.

Predictive factors for statin response in breast cancer

The well-characterized molecular and clinical heterogeneity of breast cancer warrants that for every novel drug showing efficacy against this disease, specific treatment predictive biomarkers should be identified to enable the precise selection and treatment of only those patients who may derive clinical benefit from the treatment. As such, the search for statin treatment predictive markers in breast cancer has been the subject of many studies. HMGCR has been shown to be overexpressed in about 80% of breast tumors, and its expression is correlated with less aggressive tumor phenotype and longer recurrence-free survival. (31, 32, 47) In the aforementioned clinical phase II trial when 50 breast cancer patients were treated preoperatively with atorvastatin 80mg/day for two weeks, tumor levels of Ki67 (a proliferation marker) decreased from pre-surgical biopsy to resected tumor only if the tumor expressed HMGCR, (34, 48) suggesting a predictive role for HMGCR for efficacy of statin treatment in breast cancer. HMGCR was not only differentially expressed across tumors from breast cancer patients, but was also associated with improved prognosis among ER positive breast cancer patients, whereas ER negative patients seemed to have better outcomes when HMGCR was absent.(31, 32) Several other mevalonate pathway biomarkers have been associated with breast tumor response to statins in vitro and in animal models. However, no study has comprehensively evaluated the network comprised of these individual factors, and how it is perturbed by statin exposure to alter recurrence risk. Randomized trials are now warranted to clarify the potential beneficial effects of statins in breast cancer management in the adjuvant and metastatic setting. In October 2016, the first trial with statins in metastatic breast cancer was launched, with the hypothesis that HMGCR expression will identify tumors that will respond to statin treatment (ClinicalTrials.gov Identifier: NCT02958852).

Exploring transcription profiles associated with breast cancer sensitivity to statin treatment is another method that has been explored to discover genes or gene signatures that are predictive of statin treatment sensitivity. In one such study based on *in vitro* experiments with atorvastatin in a collection of breast cancer cell lines, we aimed to uncover transcriptional differences associated with statin response in breast cancer. (24, 48) The strongest discriminants between the breast cancer cells associated with statin sensitivity at the transcriptional level were the expression of the estrogen receptor and a gene set enriched for genes involved in the cholesterol biosynthesis pathway. Following statin treatment, the less-sensitive cells exhibited the classical response of up-regulating the expression of genes in the cholesterol biosynthesis pathway *via* the normal negative feedback loop resulting from the statin-induced inhibition of HMGCR. This classical response was, however, weaker in the sensitive cells, suggesting that these cells may possess an inherent defect in this pathway. This cholesterol biosynthesis gene set showed potential for identifying tumors that experience reduced proliferation upon statin treatment, albeit in a small cohort of patients. Further studies using similar and more advanced approaches are necessary to identify robust biomarkers for identifying patients most likely to derive benefit from the addition of cholesterol-lowering

medications to their therapeutic regimen for controlling breast cancer.

